Vss	Volume of distribution of drug at steady state
WBC	White Blood Cell

1. SYNOPSIS

Name of Sponsor/Company: SiteOne Therapeutics, Inc.

Name of Investigational Product: ST-2427 for Intravenous (IV) Infusion

Name of Active Ingredient: ST-2427

Protocol Number: ST-2427-CS- **Phase:** Phase 1 **Country:** USA

001/ 5UG3 DA049599-01

Title of Study:

A Phase 1, Randomized, Double-Blind, Placebo-Controlled Single Ascending Dose Study to Evaluate the Safety, Tolerability, and Pharmacokinetics of ST-2427 IV Infusion in Healthy Subjects/Development of a Potent and Highly Selective NaV1.7 Inhibitor for the Treatment of Acute Pain with the Goal of Reducing Opioid Use and Preventing Opioid Use Disorder

Study Center(s):

Altasciences Clinical Kansas, Inc., [name]

Principal Investigator:

Studied Period (years):

Estimated date first patient enrolled: April 2021

Estimated date last patient completed: December 2021

Phase of development:

Phase 1

Objectives:

Primary: To evaluate the safety and tolerability of ST-2427 intravenous (IV) Infusion.

Secondary: To measure the pharmacokinetics (PK) of ST-2427 IV Infusion.

Study Design:

This randomized, double-blind, placebo controlled, study will be conducted to evaluate the safety, tolerability, and pharmacokinetics of ST-2427. Subjects will be randomized to receive a single dose of ST-2427 or placebo in a Single Ascending Dose (SAD) design.

A total of 30 subjects will be enrolled. Subjects will be randomized in a 4:2 ratio of ST-2427 to placebo. Study drug will be blinded to all subjects and Investigators.

Methodology:

Subjects will be enrolled into the following sequential cohorts and randomized 4:2 to receive ST-2427 or placebo:

- Cohort 1: 6 subjects will receive a single administration of placebo or ST-2427 5 mg by IV infusion over approximately 1 hour.
- Cohort 2: 6 subjects will receive a single administration of placebo or ST-2427 10 mg by IV infusion over approximately 1 hour.
- Cohort 3: 6 subjects will receive a single administration of placebo or ST-2427 15 mg by IV infusion over approximately 1 hour.

12

[figure not shown]
- Cohort 4: 6 subjects will receive a single administration of placebo or ST-2427 22 mg by IV infusion over approximately 1 hour.
- Cohort 5: 6 subjects will receive a single administration of placebo or ST-2427 33 mg by IV infusion over approximately 1 hour.

Sentinel dosing will be used in Cohort 1 in the SAD wherein the first 2 subjects (one ST-2427, one placebo) will be randomly chosen to receive study drug and be followed for up to 2 days before any other subject is dosed in that cohort. Dosing of the remaining 4 subjects (3 ST-2427, 1 placebo) in the cohort will commence after safety review by the Principal Investigator. This method of sentinel dosing of 2 subjects on the first day, followed by dosing of all remaining subjects will be used for the assessment of safety and risk mitigation. Subjects will return to the clinic for the Follow-Up visit on Day 8 ± 2 days.

C. General

Blood samples will be collected at pre-defined time points for evaluation of clinical laboratory tests (Table 4), and the PK of ST-2427. The total blood volume to be collected from each subject in this study is approximately 65.2 mL during participation in the SAD (Appendix C).

Safety and tolerability of each regimen will be assessed by adverse event (AE) monitoring, clinical laboratory tests, vital signs, body weight, electrocardiograms (ECGs), and physical examinations. Enrollment into Cohorts 2 through 5 will commence after all subjects in the prior cohort have completed the Follow-Up Visit, and safety and PK data from all prior cohorts have been reviewed by a Data Monitoring Committee (DMC) consisting of the Principal Investigator, a medical representative from the Sponsor, and a PK expert, and no clinical concerns are identified from evaluation of safety. The DMC will additionally examine all available clinical and PK data to determine the dose of ST-2427 to be administered in the next cohort.

Sample Size Justification:

Descriptive, non-inferential statistics are planned for the primary endpoint analyses. Based on clinical judgement, a sample size of 30 (20 randomized to ST-2427, and 10 randomized to placebo) is expected to be adequate to identify major treatment effects.

Number of Patients (planned):

Approximately 30 subjects

Diagnosis and Main Criteria for Inclusion:

Inclusion Criteria

Only subjects who meet the following criteria will be eligible for inclusion:

- 1. Healthy adult males and/or females (of non-childbearing potential), 18 to 55 years of age (inclusive) at the time of screening.
- 2. Body mass index (BMI) within 18.0 to 35.0 kg/m2, inclusive (minimum weight of at least 50.0 kg at Screening).
- 3. Medically healthy without clinically significant abnormalities at the screening visit, including physical examination and vital signs within the following ranges: heart rate 50 to 100 bpm, systolic blood pressure 100 to 149 mmHg; diastolic 70 to 94 mmHg.
- 4. The mean QTcF interval duration ≤450 msec for males and ≤470 msec for females measured from the triplicate ECGs taken at least 1 minute apart with QT wave corrected for heart rate (HR) using Frediricia's method.
- 5. Hemoglobin/hematocrit, white blood cell (WBC) count, and platelet count equal to or greater than the lower limit of normal range of the reference laboratory (may be confirmed upon repeat testing without Sponsor approval).
- 6. Non-smokers (including tobacco, e-cigarettes, or marijuana), and no use of any tobacco product for at least 1 month prior to admission in the study.
- 7. Willing and able to provide written informed consent.
- 8. Willing and able to comply with all study assessments and adhere to the protocol schedule.
- 9. Have suitable venous access for blood sampling, as determined by an Investigator at screening.
- 10. If female, be of non-childbearing potential (e.g. post-menopausal as demonstrated by follicle stimulating hormone (>40 mIU/mL), amenorrhea for at least one year, or surgically sterilized by tubal ligation, hysterectomy, bilateral oophorectomy and/or salpingectomy). Site personnel's review of the subject's medical records, medical examination, or medical history interview is acceptable evidence of female sterilization, verbal confirmation is adequate.
- 11. If male, willing not to donate sperm from the time of first study drug administration until 90 days after the final administration of study drug. If male and not intending to engage in sexual intercourse over the duration of the study, willing to agree to abstinence at screening. If male and engaging in sexual intercourse, willing to use a double barrier method of contraception (condom and spermicide). The latter criterion applies to all males (and/or female partners) including males who are surgically sterile and must be followed from the time of first study drug administration until 90 days after the final administration of study drug.

Exclusion Criteria

Subjects will be excluded from the study if they meet any of the following criteria:

- History or presence of significant cardiovascular (including arrhythmia and ventricular tachyphylaxis), pulmonary, hepatic, renal, hematological, gastrointestinal, endocrine, immunologic, dermatologic or neurological disease, including any acute illness or surgery within the past 3 months determined by an Investigator to be clinically relevant.
- 2. Creatinine, blood urea nitrogen (BUN), alanine aminotransferase (ALT), and aspartate aminotransferase (AST) equal to 1.5 × upper limit of normal for the reference laboratory (may be confirmed upon repeat testing).
- 3. History of orthostatic reactions.
- 4. Orthostatic reaction at screening defined as drop in systolic blood pressure by ≥20 mmHg or drop in systolic blood pressure to <90 mmHg on standing for 3 minutes from the supine position.
- 5. History of seizure disorders, except for non-complex febrile seizures in childhood with absence of non-febrile seizures in parents and siblings.
- 6. Positive urine drug/alcohol testing at Screening or Day –2.
- 7. Positive test results for HIV-1/HIV-2 Antibodies, Hepatitis B surface Antigen (HBsAg) or Hepatitis C Antibody (HCVAb).
- 8. Positive test results for COVID-19 (PCR or Antibodies)
- 9. History of substance abuse or alcohol abuse (defined as greater than 2 standard drinks per day) within the previous 2 years.
- 10. Use of any prescription medication or any over-the-counter medication, including herbal products and vitamins within 14 days or 5 half-lives (whichever is longer) prior to randomization.
- 11. Documented hypersensitivity reaction or anaphylaxis to any medication.
- Blood donation (excluding plasma donation) of approximately 500 mL within 56 days prior to 12. Screening, or receipt of a blood transfusion within 1 year of Screening.
- 13. Plasma donation within seven days prior to screening.
- 14. Dosed in another investigational clinical trial within 30 days prior to Screening.
- Any condition or prior therapy, e.g., seizures, or head trauma, that may lead to CNS effects during 15. the study.
- 16. Documented or self-reported history of orthostatic hypotension or symptoms of hypotension such as dizziness, syncope, or blurred vision upon standing.
- Any condition which is associated with increased brain permeability, e.g., cerebral ischemia, 17. brain trauma, multiple sclerosis, brain tumors, brain infection.

Investigational Product, Dosage and Mode of Administration:

In all cohorts, study drug (ST-2427 or placebo) will be infused via IV over 1 hour. Subjects will be randomized 4:2 to receive a single dose of ST-2427 or placebo.

Subjects randomized to ST-2427 in Cohort 1 will receive 5 mg ST-2427 as a single IV infusion over one hour. The starting dose of 5 mg will be administered to all subjects in Cohort 1 regardless of body weight.

The doses of ST-2427 to be administered in all cohorts after Cohort 1 will be approved by the DMC following examination of all available clinical and PK data. In the SAD, the dose increase of

ST-2427 from Cohort 1 onwards is <2-fold from the prior cohort,

In all cohorts, placebo will be administered as 1-hour IV infusions at matching volumes and times to those administered to subjects randomized to ST-2427 in the same cohort.

Details of study drug preparation are provided in the Pharmacy Manual for this study.

Duration of Treatment:

Single 1-hour IV infusion

Reference Therapy, Dosage, and Mode of Administration:

Placebo (5% Dextrose Injection, USP) will be administered by 1-hour IV infusions at the same volume and rate as used for ST-2427

Criteria for Evaluation:

Safety:

Safety measures include incidence and severity of AE's, physical examination

body weight, ECG, clinical laboratory testing (chemistry, hematology, urinalysis), respiratory rate, body temperature, oxygen saturation, local (injection site) irritation, and QTcF measures.

Pharmacokinetics:

Blood and urine samples will be collected at specified times during the study for measurement of ST-2427 concentration using a validated analytical method. The measured concentrations will be used for PK modeling.

Statistical Methods:

Treatment effects on safety and tolerability will be evaluated using descriptive statistics (mean, standard deviation, median, minimum, maximum) of the number and proportion of subject experiencing adverse events by system organ class, and preferred term.

Prior to dosing on Day 1, three separate measurements of supine BP (including DBP, SBP) and HR will be recorded one minute apart after at least 5 minutes rest. These repeat assessments will be used for analyses of change from baseline for these measures.

Cardiodynamic evaluation will be performed to evaluate the treatment effects on heart rate-corrected QT interval using the Fridericia (QTcF) corrections, using concentration-QTc analysis, and on other ECG parameters (heart rate, PR and QRS interval and treatment emergent T and U-wave abnormalities). The statistical analysis will be detailed in a separate SAP.

For purposes of monitoring safety, treatment-emergent adverse events (AEs) will be graded using the Toxicity Grading Scale for Healthy Adult and Adolescent Volunteers (FDA 2007) which is appropriate for healthy subjects.

Descriptive statistics will be used to evaluate the treatment effects on clinical laboratory assessments including clinical chemistry, hematology, and urinalysis.

PK modeling will be performed using compartmental methods. PK parameters such as, but not limited to C_{max} , T_{max} , Volume of distribution, Elimination half-life, and AUC after the ST-2427 infusion in the SAD. Descriptive statistics will be used to summarize PK parameters, and ST-2427

Confidential and Proprietary

concentrations in the urine by cohort. In addition, exploratory analyses of the effects of some baseline characteristics (e.g., sex, body weight) on PK parameters may be undertaken.

2. INTRODUCTION

This is a Phase 1, randomized, double-blind, placebo-controlled study in healthy adult males and females of non-child-bearing potential to evaluate the safety, tolerability, and pharmacokinetics (PK) of ST-2427.

SiteOne Therapeutics, Inc. plans to use the safety, tolerability, and PK findings from this study to inform the doses and study design for Phase 2 clinical studies in subjects with acute post-operative pain.

Approximately 30 subjects, 6 subjects into each of 5 cohorts, will be enrolled in this study at a single clinical site.

Subjects will be randomized 4:2 to receive a single dose of ST-2427 or placebo in a Single Ascending Dose (SAD) design. The study will evaluate 5 dose strengths of ST-2427, infused intravenously (IV) over 1 hour; one dose level in each of 5 cohorts of subjects.

2.1. Indication

SiteOne Therapeutics, Inc. plans to develop ST-2427, a novel, selective, state-independent inhibitor of the voltage-gated sodium channel isoform Nav1.7, for treatment of acute postoperative pain and sparing of opioids. Study ST-2427-CS-001 is the first-in-human study, and aims to evaluate the safety, tolerability, and PK of ST-2427 when administered at increasing dose strengths/durations to healthy volunteers.

An estimated 80% of patients who undergo surgery experience acute postoperative pain that is typically moderate, severe or extreme in nature (Chou 2016), a majority of whom have inadequate pain control which negatively impacts quality of life, recovery of function, the risk of persistent postsurgical pain, and morbidity and mortality due to post-surgical complications (Apfelbaum 2003, Sharrock 1994, Katz 1996, Kehlet 2006). Effective postoperative pain control is essential to enhance patient comfort, earlier mobilization, fewer pulmonary and cardiac complications, reduced risk of deep vein thrombosis, faster recovery, less likelihood of developing neuropathic pain and reduced cost of care (Ramsay 2000).

The American Pain Society, the American Society of Regional Anesthesia and Pain Medicine, and the American Society of Anesthesiologists (Chou 2016) recommends the use of opioids, non-steroidal anti-inflammatory drugs (NSAIDs) and/or acetaminophen, gabapentin or pregabalin, ketamine (IV) for management of postoperative pain in conjunction with appropriate

18

patient education, real-time pain evaluation/scoring, and other analgesia modalities including transcutaneous electrical nerve stimulation.

Opioids in particular are associated with dose-limiting side effects, such as confusion, drowsiness, nausea, respiratory depression and the potential for dependence and abuse (Kelly 2008). The alarming level of opioid abuse in the United States (US) has led some to focus on multimodal pain management approaches that decrease or eliminate the use of opioids altogether (Wardhan 2017). Key to this approach is the need to develop new, effective non-opioid analgesic therapies.

[figure not shown]
Human and animal genetic and pharmacology data support Na_v1.7 as a promising target for the development of non-opioid pain therapeutics. Na_v1.7 is preferentially expressed in peripheral somatic and visceral sensory neurons within the dorsal root ganglion, including nociceptors, olfactory sensory neurons, and sympathetic ganglion neurons (*Dib-Hajj 2013*, *Dib-Hajj 2017*). Conditional, or global deletion of Na_v1.7 in mice led to reduction or loss of inflammatory pain responses induced by a range of stimuli (*Nassar 2004, Yeomans 2005, Minett 2012, Gingras 2014*). Congenital insensitivity (indifference) to pain (CIP) in humans is linked to loss-of-function mutations in both alleles of SCN9A, the gene encoding Na_v1.7 (*Cox 2006*). By contrast, dominantly inherited gain-of function missense mutations in SCN9A are found in patients with inherited erythromelalgia (IEM) and paroxysmal extreme pain disorder (PEPD), who report flushing and severe, episodic pain triggered by mild warmth or exercise (in IEM) or bowel movement (in PEPD) (*Yang 2004, Fertleman 2006*).

[figure not shown]
2.2. Nonclinical Experience with ST-2427

ST-2427 is a highly selective, state-independent inhibitor of human voltage-gated Na⁺ ion channel 1.7 (Na_V1.7) intended for the treatment of acute, postoperative pain.

Confidential and Proprietary

[figure not shown]

[figure not shown]

Protocol ST-2427-CS-001 SiteOne Therapeutics, Inc.

5UG3 DA049599-01 (Amendment 3)

[figure not shown]
FINAL 25 June 2021

Protocol ST-2427-CS-001/ 5UG3 DA049599-01 (Amendment 3) SiteOne Therapeutics, Inc.

FINAL 25 June 2021

Primary Objective 2.3.

The primary objectives of the study are to evaluate the safety and tolerability of ST-2427 IV Infusion.

Secondary Objectives 2.4.

The secondary objective of the study is to measure the PK of ST-2427 IV infusion.

3. INVESTIGATIONAL PLAN

3.1. Overall Study Design

Owing to its cationic nature, ST-2427 has low cellular permeability and is expected to have low bioavailability in humans if administered orally. As such, ST-2427 will be administered via IV in this trial. Furthermore, study drug will be administered slowly over a 1-hour infusion to mitigate/eliminate the number and severity of clinical observations which, in rats and monkeys, were generally observed at the time of highest drug concentration.

Subjects will be enrolled into the following sequential cohorts and randomized 4:2 to receive ST-2427 or placebo:

3.1.1. Single Ascending Dose Phase (SAD)

Cohort	Dose mg	Fold Increase from Previous Cohort	Predicted Peak Concentration ng/mL
1	5	_	200
2	10	2	375
3	15	1.5	565
4	22	1.5	820
5	33	1.5	1190

Subjects will be asked to participate in this study for a period of approximately 5 weeks: 4 weeks of Screening, 1 day of study treatment, 1 week of follow-up.

Sentinel dosing will be used in Cohort 1 wherein the first 2 subjects (one ST-2427, one placebo) will be randomly chosen to receive study drug and be followed for up to 2 days before any other subject is dosed in that cohort. Dosing of the remaining 4 subjects (3 ST-2427, 1 placebo) in the cohort will commence after safety review by the Principal Investigator and Sponsor. Study assessments will be performed at the days/times defined in Table 4. Subjects enrolled in the SAD will return to the clinic for additional assessments and sample collections at approximately 8 days (± 2 days) after the start of infusion.

3.1.2. General

Eligible subjects will be scheduled to return to the clinic and be admitted for a confinement period of 3 days in the SAD. The confinement period will begin the day before the start of study

drug administration to confirm eligibility for the study and for the completion of baseline assessments.

Subjects will return to clinic on Day 8 ± 2 days for the Follow-Up visit.

Safety and tolerability of each regimen will be assessed by adverse event (AE) monitoring, clinical laboratory tests, vital signs, body weight, electrocardiograms (ECGs), and physical examinations. Enrollment into Cohorts 2 through 5 will commence after all subjects in the prior cohort have completed the Follow-Up visit, and safety and PK data from all prior cohorts have been reviewed by a Data Monitoring Committee (DMC) consisting of the Principal Investigator, a medical representative from the Sponsor, and a PK expert, and no clinical concerns are identified.

3.2. Number of Subjects

Approximately 30 subjects will be enrolled into this study, 6 subjects in each of the 5 cohorts.

3.3. Treatment Assignment

Subjects who meet all criteria for enrollment will be randomly assigned to 1 of 2 treatment groups, ST-2427 or placebo, following a 4:2 allocation. A randomization schedule will be produced by an unblinded statistician using a validated computer program. Once baseline data (Day –1) has been reviewed and subjects are determined to be eligible for the study, they will be assigned a unique randomization number. Investigators and subjects will remain blinded to the study drug assignment and only certain designated staff (such as pharmacy personnel) will be unblinded to study treatment.

Sealed code break envelopes will be provided by an unblinded statistician prior to the start of the study. During the study, the blind is to be broken by an Investigator only when subject safety is at risk and unblinding must occur to determine effective medical intervention for the subject. All unscheduled unblinding events must be reported to the medical monitor and SiteOne Therapeutics, Inc. as soon as possible.

[figure not shown]
3.4. Dose Adjustment Criteria

The dose levels have been selected to reach defined peak concentrations as predicted from PK parameters in animal studies. If it is found in the initial study cohort that the achieved peak concentrations at a group level deviate from the predictions, doses will be adjusted accordingly

in subsequent cohorts to achieve the defined peak concentrations. All subjects will receive the dose defined for the cohort to which they were randomized.

3.4.1. Safety Criteria for Adjustment or Stopping Doses

The following stopping criteria will be used to inform decisions to continue drug infusion in any given subject:

3.4.2. Pharmacokinetic Criteria for Adjustment or Stopping Doses

If it is found in the initial study cohort that the achieved peak concentrations at a group level deviate from the predictions, doses will be adjusted accordingly in subsequent cohorts to achieve the defined peak concentrations.

3.5. Criteria for Study Termination

The study will run to completion unless the Sponsor decides to terminate it earlier, e.g., following a recommendation from the DMC based on review of all available PK and safety data.

Confidential and Proprietary Page 28 of 62

 Table 4:
 Schedule of Assessments in Part A (Single Ascending Dose)

	Screening		CONFINEMENT Follow- Up/EOS/ET																			
Time (days)	-28 to -2	-1		1 2 3									8± 2									
Time ^a (hours)			Pre- dose	0	0.25	0.5	0.75	1	1.15	1.3	1.5	2	2.5	3	4	6	8	10	12	24	8	
Informed consent	X																					
Medical/medication history	х	х																				
Physical Examination	x	х																			x b	x
Weight, height, BMI	Х	X																				
Serum Pregnancy Test	Х	X																				
Local Irritation at the infusion site						х														х		
HIV, hepatitis B, hepatitis C testing	Х																					
COVID-19 testing ^f		X																				
Follicle stimulating hormone ^g	x																					
Review inclusion/exclusion	x	Х																				
Randomization		X																				
Admission to clinic		X																				
Confinement ^h										X												
Discharge from clinic																					X	
Adverse events		1								X												
Concomitant Medications	х										2	ζ										
Study drug				х																		
administration ⁱ																						
LABORATORY MEAS	URES	1					1	1	ı	1	1			1		1	,		1	1	1	1
Urine drug and alcohol tests	x	Х																				
Clinical chemistry	х	X		ļ																X	X	X
Hematology	Х	X																	 	X	X	X
Coagulation tests	X		1																			
Urinalysis	Х	X																	 	X		Х
Blood PK sample ^j	İ		X	1	X	X	X	X	X	X	X	X	X	X	X	X	X	X	X	X	X	İ

Protocol ST-2427-CS-001/ SiteOne Therapeutics, Inc.

5UG3 DA049599-01 (Amendment 3)

FINAL 25 June 2021

Confidential and Proprietary Page 29 of 62

	Screening								CON	NFINE	MENT	,										Follow- Up/EOS/ET
Time (days)	-28 to -2	-1								1										2	3	8± 2
Time ^a (hours)			Pre- dose	0	0.25	0.5	0.75	1	1.15	1.3	1.5	2	2.5	3	4	6	8	10	12	24	4 8	
Urine PK sample ^k			X						X						2		:	X	Х	X	X	

- a Time is defined relative to the start of the first infusion of study drug. For example, an assessment scheduled to occur at time = 2 hour must be performed 2 hours after the start of study drug infusion, i.e., 1 hour after the end of the infusion.
- **b** A symptom-directed physical exam will be conducted prior to discharge.

Orthostatic tests will be performed pre-dose (within 60 minutes prior to study drug administration), and at 0.5, 1, 1.5, 2, and 2.5 hours (± 10 minutes) after start of infusion. For these tests, subjects should be standing for 3 minutes with measurements of heart rate and blood pressure (SBP, DBP) at 1, 2, and 3 minutes after standing

- d e
- f COVID-19 test will be performed after Screening is complete and subject is confirmed, but prior to check-in to the unit
- g A blood sample will be collected from women and tested for follicle stimulating hormone to confirm eligibility for this study unless documented evidence of surgical sterilization is available and reviewed by qualified study personnel.
- h Subjects will be confined at the clinic from the day before study drug infusion through at least 48 hours after the start of study drug infusion. This is predicted to exceed the time necessary for the concentration of ST-2427 to decrease to <5% of the peak concentration. During the study, the period of confinement may be extended if the drug elimination is found to be slower than predicted in the first cohort(s). Subjects will be discharged only if clinically significant AEs, if any, are resolved.
- i Study drug is to be administered intravenously as a 1-hour infusion. A ±10-minute window is allowed for the duration of infusion, and a ±15-minute window is allowed for the start of infusion relative to the nominal time.
- j Whole blood samples collected for PK analysis should be collected at the specified time. When blood sample collections coincide with other assessments, assessments should be conducted in the following orders for PK will be collected at the following time points:
 - Day 1: pre-dose, and 0.25, 0.5, 0.75, 1, 1.15, 1.3, 1.5, 2, 2.5, 3, 4, 6, 8, 10, 12, 24, 48
 - Predose PK samples should be collected within approximately 60 minutes prior to dosing
- k A pre-dose urine sample will be collected at any time prior to dosing on Day 1 for analysis of pre-dose ST-2427 concentrations in the urine. Subjects are to be instructed to empty their bladders prior to dosing on Day 1. All urine will be collected for interval analysis of PK from the start of the first infusion until at least 48 hours later. Urine will be pooled 0 hr 4 hr, 4 hr 8 hr, 8 hr 12 hr, 12 hr 24 hr, and 24 hr 48 hr collection windows and the collection time and volume for each collection recorded. Pooled urine samples will be maintained refrigerated and processed at the end of each pooled collection.

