5. TREATMENT OF SUBJECTS

5.1. **Description of Study Drug**

Table 5: **Investigational Product**

	Investigation	onal Product
Product Name:	ST-2427 for IV Infusion	Placebo (5% Dextrose Injection, USP)
Dosage Form:	Sterile Solution	Sterile Solution
Unit Dose (by Cohort)	250 mL total volume 1: 5 mg ST-2427 2: 10 mg ST-2427 3: 15 mg ST-2427 4: 22 mg ST-2427 5: 33 mg ST-2427	0 mg/mL
Route of Administration	Intravenous Infusion	Intravenous Infusion
Physical Description	Clear, colorless solution	Clear, colorless solution
Manufacturer	AMRI, Albany, NY Sterile solution will be prepared by Alta Sciences	Sourced by Alta Sciences

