5.2. Concomitant Medications

No concomitant therapy is allowed between the start of confinement through the completion of the Follow-up visit. In addition, subjects are disqualified from participation in this study if they used any prescription medication or any over-the-counter medication, including herbal products and vitamins within 14 days or 5 half-lives (whichever is longer) prior to randomization.

5.3. **Treatment Compliance**

All study drug will be administered to all subjects by qualified site personnel during the confinement period. As such, treatment compliance is not relevant to this study. Missed doses will be assumed to be for reasons of subject safety, withdrawal, dosing error or other protocol deviation.

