8.1.5. Local Injection Site Irritation

Consistent with Food and Drug Administration (FDA) guidance, *Guidance for Industry Toxicity Graading Scale for Healthy Adult and Adolescent Volunteers Enrolled in Preventative Vaccine Clinical Trials, (2007)*, the assessment of local irritation at the injection site will be performed at the visits noted in Table 4 and Appendix D. The scale consists of 4 categories with each graded on a scale from 1 to 4 based on clinical abnormality. The scale is provided in Appendix D.

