APPENDIX D:

TABLE FOR CLINICAL ABNORMALITIES ASSOCIATED WITH LOCAL REACTION TO INJECTABLE PRODUCT

Mild (Grade 1)	Moderate(Grade 2)	Severe (Grade 3)	Potentially Life Threatening (Grade 4)
Does not interfere with activity	Repeated use of non- narcotic pain reliever > 24 hours or interferes with activity	Any use of narcotic pain reliever or prevents daily activity	Emergency room (ER) visit or hospitalization
Mild discomfort to touch	Discomfort with movement	Significant discomfort at rest	ER visit or hospitalization
2.5 – 5 cm	5.1 – 10 cm	> 10 cm	Necrosis or exfoliative dermatitis
2.5 – 5 cm and does not interfere with activity	5.1 – 10 cm or interferes with activity	> 10 cm or prevents daily activity	Necrosis
	Does not interfere with activity Mild discomfort to touch 2.5 - 5 cm 2.5 - 5 cm and does not interfere	Does not interfere with activity Mild discomfort to touch 2.5 - 5 cm 2.5 - 5 cm and does not interfere Repeated use of non-narcotic pain reliever > 24 hours or interferes with activity Discomfort with movement 5.1 - 10 cm 5.1 - 10 cm or interferes with	Does not interfere with activity Does not interfere with activity Repeated use of non-narcotic pain reliever > 24 hours or interferes with activity Mild discomfort to touch Discomfort with movement Significant discomfort at rest > 10 cm > 10 cm

In addition to grading the measured local reaction at the greatest single diameter, the measurement should be recorded as a continuous variable.

^{**} Induration/Swelling should be evaluated and graded using the functional scale as well as the actual measurement.

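### Infusion-site irritation has no scheduled score before dosing, none fixed at the end of infusion, and none between the infusion and 24 h, so a late or short-lived reaction would get no standard grade

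*Combined protocol and SAP*

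**What the plan says.** - **Timing.** In Table 4 (Schedule of Assessments), the row "Local Irritation at the infusion site" has two marks. Section 8.1.5 states that "the assessment of local irritation at the injection site will be performed at the visits noted in Table 4 and Appendix D". Appendix D holds grading criteria only. It lists no visit or hour.
- **Clock.** Table 4 footnote a: "Time is defined relative to the start of the first infusion of study drug". So 0.5 h lies within the infusion and 1 h is its nominal end. Footnote i: "A ±10-minute window is allowed for the duration of infusion".
- **Volume.** Table 5 gives "250 mL total volume" for every ST-2427 cohort.
- **Role.** The synopsis lists local irritation among the safety measures, under the primary objective of safety and tolerability.
- **Scale.** Section 8.1.5 describes four categories graded 1 to 4, and the notes to Appendix D ask for the measured diameter as well. Grade 2 in its first row reads "Repeated use of non- narcotic pain reliever > 24 hours or interferes with activity". Grade 3 in that row is any narcotic analgesic use, or prevention of daily activity.
- **Concomitant therapy.** Section 5.2: "No concomitant therapy is allowed between the start of confinement through the completion of the Follow-up visit".

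**The concern.** This is a first-in-human intravenous product, and site tolerability is something the trial sets out to describe. The volume is fixed while the dose rises, so the infused solution becomes more concentrated in each cohort. A dose-related site effect is therefore a fair question, and section 9.7 has the DMC review safety data before each cohort opens.

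A graded local score is useful when every subject is inspected at the same times with the same ruler. If the only scores are taken during the infusion and the next day, a reaction that appears near or after the end of infusion and settles overnight leaves no scheduled grade or diameter. Without a pre-dose score, redness or tenderness from the cannula cannot be subtracted within a subject, and each cohort has only two placebo subjects to show it between groups.

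**Working it through.** The plan states no figure to reproduce. The check is a reading of one table row followed by simple arithmetic.

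**1. Where the marks fall.** The Table 4 header has a label column and 22 time columns. The irritation row has the same number of fields, and counting across puts its marks under 0.5 h and 24 h. Other rows support the count: the study-drug mark falls at 0 h, and the urinalysis marks fall at Screening, Day -1, 24 h and Follow-Up, as section 8.1.7.3 says.

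**2. How far the count can be trusted.** Single-column marks are reliable, but merged cells are not. The 0 to 4 h urine pool spans 12 columns (0, 0.25, 0.5, 0.75, 1, 1.15, 1.3, 1.5, 2, 2.5, 3 and 4 h), and its mark appears under 1.15 h, the sixth of them, near the middle. A cell merged over 0, 0.25, 0.5, 0.75 and 1 h has its exact middle at 0.5 h. A cell covering all of confinement is unlikely, because the confinement and adverse-event marks fall under 1.3 h. Two readings therefore remain.

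| | Score at 0.5 h | One cell covering 0 to 1 h |
|---|---|---|
| Pre-dose score | none | none |
| Score fixed at end of infusion | none | none (any time in the hour would comply) |
| Unscored interval before 24 h | 24 − 0.5 = 23.5 h | 24 − 1 = 23 h |
| Blood PK times inside that interval | 13 (0.75 to 12 h) | 11 (1.15 to 12 h) |
| Score at 48 h or Follow-Up | none | none |

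**3. What a 0.5 h score would see.** Assume a constant rate and a total of 250 mL. The volume infused at 30 min is 250 × 30 / duration.
- 50 min: 150 mL (60%). From end of infusion to the 24 h score: 24 − 50/60 = 23.2 h.
- 60 min: 125 mL (50%). Interval: 23.0 h.
- 70 min: 107 mL (43%). Interval: 22.8 h.

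**4. Illustration of what is missed.** Assume onset is uniform over the 1 h infusion. This is an assumption, as the documents give no onset or duration data.
- Scores at 0.5 h and 24 h: for reactions lasting from 0.5 h to 23 h, only those with onset by 0.5 h are present at a score, so 0.5 / 1 = 50%.
- With a score at 1 h added: 100% for the same durations.
- Reactions lasting 24 h or more: 100% under the present schedule.
- Under the merged-cell reading, a single score at time s within the hour finds a share s of reactions that last at least s and end before 24 h. The share depends on when in the hour staff happen to look.

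A reaction that begins after the infusion and is gone by 24 h is missed by the scheduled scores on either reading.

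**5. Concentration across cohorts.** 5 mg / 250 mL = 0.02 mg/mL in Cohort 1 and 33 mg / 250 mL = 0.132 mg/mL in Cohort 5, a ratio of 6.6.

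**6. Appendix D beside section 5.2.** Analgesic use appears in one of the four rows, at Grades 2 and 3, each time with an activity-based alternative. Section 5.2 permits no concomitant therapy in the period when scores are taken. In addition, more than 24 h of analgesic use for a reaction to the infusion cannot have built up by a score 24 h after the infusion began. The two passages do not fit together, although neither grade is closed off.

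**The case against.** The strongest objection is that the schedule may be misread: if the first mark is a merged 0 to 1 h cell, the end of infusion may be covered. That stands, and it rules out stating flatly that the end of infusion goes unscored. It does not supply a pre-dose score, a fixed time, or any score between the infusion and 24 h.

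A reader might also infer that a reaction between scores is never graded. The documents do not support that. Section 8.4 records events that are reported, elicited or observed, with onset, resolution and a graded intensity. Section 9.1 grades adverse events on the FDA 2007 scale, the guidance that section 8.1.5 cites for Appendix D. Subjects are confined for at least 48 h after the infusion starts, with frequent staff contact. What adverse-event capture does not require is a site inspection and diameter in every subject at a common time.

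A reader might tie site reactions to peak drug level, because section 3.1 says findings were "generally observed at the time of highest drug concentration". That sentence concerns clinical observations in rats and monkeys and says nothing about the infusion site, so it is not relied on here.

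A reader might further conclude that the concomitant-therapy rule makes Grades 2 and 3 unreachable, or that the analgesic criteria should be struck out. Neither follows. The activity alternatives remain, three of the four rows do not use analgesics, and prohibited use that did occur would still count.

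Finally, placebo is a matched-volume infusion, so cannula effects can be compared between arms. That is true, but with two placebo subjects per cohort (10 overall) a within-subject baseline still adds information.

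**Conclusion.** The point holds as a gap in the standardised measure, not in safety capture as a whole. On either reading of Table 4 there is no pre-dose score, no score fixed at the end of infusion, and an interval of 23 to 23.5 h with no scheduled score before 24 h. A reaction that arises late in the infusion or after it and fades overnight would be known only as an adverse event, without an Appendix D grade and diameter at a common time for comparison with placebo and across cohorts. How often this would happen is unknown. The 50% in the illustration rests wholly on the assumed uniform onset. The 0.5 h position rests on extracted text and needs checking against the original. The mismatch between Appendix D and section 5.2 is secondary: it calls for reconciliation and does not show that reactions would be under-graded. This is a worthwhile, inexpensive improvement rather than a flaw that undermines the trial.

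**What to change.** 1. Check the irritation row of the original Table 4, and state the intended hours explicitly if the first mark is a merged cell.
2. Add scores at pre-dose, at 1 h (end of infusion) and at one later Day 1 PK time such as 4 h, and keep the existing times. Because the infusion may run 50 to 70 min, record the actual time of the 1 h score relative to the end of infusion.
3. Report change from the pre-dose score by treatment and cohort, for grade and for diameter.
4. In section 8.1.5, stop citing Appendix D as a source of visit times. It remains the source of the scale.
5. Ask the sponsor to reconcile the analgesic-use criteria in the first row of Appendix D with section 5.2. This review takes no position on which should change.

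Cost: an amendment to one Table 4 row and one short section, plus three brief site inspections per subject. PK blood draws are already scheduled pre-dose, at 1 h and at 4 h, so staff will be at the bedside.
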